10.1.4 Clinical Laboratory Assessments

Clinical laboratory assessments include:

Hematology: red blood cell count (RBC), white blood cell (WBC with differentials) [L/H*]: WBC, neutrophils, lymphocytes][H: remaining differentials], hemoglobin (Hgb) [L/H], hematocrit (Hct), mean corpuscular volume (MCV), mean corpuscular hemoglobin (MCH), mean corpuscular hemoglobin concentration (MCHC), red blood cell distribution width, platelet count [L/H], coagulation - prothrombin time (PT) [H], partial thromboplastin time (PTT) [H], international normalized ratio (INR) [H]. Both counts and percentages will be reported for WBC differentials.

Serum chemistry: sodium (Na) [L/H], potassium (K) [L/H], chloride (Cl) [L/H], bicarbonate (HCO3) [L/H], blood urea nitrogen (BUN) [H], glucose [L/H], calcium (Ca) [L/H], magnesium (Mg) [L/H], phosphorus [L/H], total protein [L/H], triglycerides [H], total cholesterol [H], high density lipoprotein (HDL) [L], low density lipoprotein (LDL) [H], urea, creatinine [H], total bilirubin [H], aspartate aminotransferase (AST(SGOT)) [H], alanine aminotransferase (ALT(SGPT)) [H], alkaline phosphatase (ALP) [H], uric acid [H]

Urinalysis (dip-stick test): Specific gravity, pH, glucose [H], protein, ketones, blood [H]

*[L], [H], and [L/H] denote those tests that will have worst case low, high, and low & high summary respectively.

All test results and associated normal ranges from central laboratories will be reported in the standard International System of Units (SI unit). Continuous values will be summarized using descriptive statistics and categorical values, including low, normal, and high results with respect to reference ranges will be tabulated at each visit and treatment group. Change from Baseline for continuous values will be summarized using both continuous summary statistics as well as shift tables based on normal ranges at each post-Baseline visit. Shift from Baseline tables will also include shift from Baseline to the worst case post-Baseline. Boxplots will be presented for each quantitatively measured hematology, chemistry, and urinalysis analyte over time, with a separate boxplot for each treatment group.

Note that subjects under the original Protocol at the Transplantation Visit will have laboratory assessments at 16 and 42 hours post-transplantation; subjects under Amendment 1 of the Protocol at the Transplantation Visit will have laboratory assessments at 16 hours post-transplantation. Additionally, subjects under Amendment 1 of the Protocol at Visit 3 (Pre-Transplantation Week 8 – 10) will have a urinalysis assessment; subjects under the original Protocol will not.

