6.4.2. Exclusion Criteria

Study subjects meeting any of the following criteria during screening evaluations will be excluded from entry into the study:

1. Prior stem cell therapy of any kind.
2. Inability to lie flat for the duration of intrathecal cell transplantation and/or bone marrow biopsy, or inability to tolerate study procedures for any other reason.
3. History of autoimmune disease (excluding thyroid disease) myelodysplastic or myeloproliferative disorder, leukemia or lymphoma, whole body irradiation, hip fracture, or severe scoliosis.
4. Any unstable clinically significant medical condition other than ALS (e.g., within six months of baseline, had myocardial infarction, angina pectoris, and/or congestive heart failure), treatment with anticoagulants that, in the opinion of the investigator, would compromise the safety of patients.
5. Any history of malignancy including any malignancy affecting the central nervous system and melanoma, within the previous 5 years, with the exception of localized skin cancers (with no evidence of metastasis, significant invasion, or re-occurrence within three years of baseline).
6. Serum AST or ALT value >3.0 times the upper normal limit.

7. Serum creatinine value >2.0 times the upper normal limit.
8. Positive test for Hepatitis B, Hepatitis C, HIV.
9. Current use of immunosuppressant medication or use of such medication within 4 weeks of Screening visit (Visit 1).
10. Any history of acquired or inherited immune deficiency syndrome.
11. Exposure to any other experimental agent (off-label use or investigational) or participation in a clinical trial within 30 days prior to Screening Visit (Visit 1).
12. Use of non-invasive ventilation (NIV), diaphragm pacing system or invasive ventilation (tracheostomy).
13. Any history of either substance abuse within the past year, or unstable psychiatric disease according to PI judgment.
14. Placement or usage of feeding tube.
15. Pregnant women or women currently breastfeeding.

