6.5.3.4. Visit 4: Bone Marrow Aspiration (Week 9-11)

Once all safety test results are confirmed negative or normal, all participants will undergo:

- Review of concomitant medications
- Review of adverse events
- Vital sign measurements

After these assessments, all participants will undergo bone marrow aspiration (BMA) by a credentialed health care provider as per Medical Centre procedures from multiple punctures of the iliac crest of the patients' pelvic bone.

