10.1 Safety Analyses

Safety will be assessed based on the incidence of adverse events (AEs) and clinically relevant changes in vital signs, clinical laboratory assessments (hematology, serum chemistry, and urinalysis), physical and neurological examinations, and ECG tests. Safety analyses will be based on the Safety population. Each safety parameter will be listed by subject.

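### The laboratory tables count subjects only against the reference range, so the plan has no by-arm count of subjects by size of rise in AST, ALT or creatinine

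*SAP*

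**What the plan says.** SAP 10.1 sets the standard: "Safety will be assessed based on the incidence of adverse events (AEs) and clinically relevant changes in vital signs, clinical laboratory assessments", together with examinations and ECG.

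SAP 10.1.4 then plans the following laboratory output:

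- Descriptive statistics of the measured values, and counts by category, "including low, normal, and high results with respect to reference ranges will be tabulated at each visit and treatment group".
- Two kinds of summary for the change since baseline: continuous statistics, and "shift tables based on normal ranges at each post-Baseline visit".
- A version of the same shift table that takes each subject's worst later value.
- Boxplots over time for each quantitative analyte, one per arm.

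SAP 10.1 adds by-subject listings. Protocol 6.8.1.7 asks investigators to record laboratory abnormalities that they judge clinically significant as adverse events.

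The exclusion criteria in Protocol 6.4.2 bear on who may enter with raised values. For liver enzymes the limit is "Serum AST or ALT value >3.0 times the upper normal limit"; for renal function it is "Serum creatinine value >2.0 times the upper normal limit". Protocol 6.5.3.4 then opens the marrow aspiration visit with a condition: "Once all safety test results are confirmed negative or normal, all participants will undergo".

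For ECG, SAP 10.1.5 counts subjects by size: QTcF changes above 30 and above 60 msec, and values above 450 msec.

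**The concern.** An incidence needs a defined event. SAP 10.1 calls for clinically relevant laboratory changes, but SAP 10.1.4 does not say what size of change counts. The only laboratory categories are those of the reference range, which record the side of a limit and not the distance from it. No multiples of ULN, multiples of baseline or toxicity grades are specified.

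The gap reaches two groups. In a subject who is high at baseline, no rise of any size registers as a shift. In a subject who is normal at baseline, a trivial excursion and a tenfold one register identically, and a doubling within the range does not register at all. The second group matters however many subjects start high.

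At stake is whether the clinical study report can state, by arm, how many subjects had a substantial hepatic or renal change without relying on investigator judgement.

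**Working it through.** **1. The plan's own safety figure.** SAP 5 gives a 95% probability of seeing an adverse event with a true rate of 8% among 36 active subjects. Check: 1 - 0.92^36 = 0.950. It reproduces and is not in dispute. It concerns seeing at least one event, so it presupposes that the event is defined.

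**2. What each table records.** Illustrative values in multiples of ULN:

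| Baseline to worst | Ratio to baseline | Shift table | Count by size |
|---|---|---|---|
| AST 1.5 to 9 | 6.0 | high to high, no shift | counted (above 3 x ULN) |
| AST 0.95 to 1.01 | 1.06 | normal to high | not counted |
| ALT 0.95 to 10 | 10.5 | normal to high, same cell as the row above | counted (above 3 x ULN) |
| Creatinine 0.45 to 0.90, both in range | 2.0 | normal to normal, no shift | counted (twice baseline) |

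If the first row is one of 36 active subjects, the arm mean moves by (9 - 1.5)/36 = 0.21 x ULN. The mean would hide it. The maximum change would probably show it.

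**3. Shifts expected from an inert product.** Inputs from the documents:

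- 36 active and 12 placebo subjects (SAP 5).
- Baseline is the latest value available before transplantation (SAP 8.2). This is normally Visit 3, because Protocol Table 2 has no pre-dose chemistry at Visit 5.
- Five later draws under Amendment 1: 16 hours, then Weeks 4, 8, 16 and 24 (Protocol 6.5.1 and Tables 1 and 2). The extra 42-hour draw under the original protocol is left out; it would raise the figures slightly.

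Assumptions, because the documents give neither: a 95% reference range (2.5% above the upper limit) and a normally distributed analyte with equal correlation between all pairs of draws.

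With independent draws, the probability of being not high at baseline and high at the worst later draw is 0.975 x (1 - 0.975^5) = 0.975 x 0.119 = 0.116. For correlated draws, a simulation of 400,000 subjects gives:

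| Correlation | Probability per analyte | Expected of 36 | Expected of 12 |
|---|---|---|---|
| 0 | 11.6% | 4.17 | 1.39 |
| 0.5 | 7.9% | 2.84 | 0.95 |
| 0.7 | 5.7% | 2.04 | 0.68 |
| 0.8 | 4.4% | 1.58 | 0.53 |
| 0.9 | 2.9% | 1.04 | 0.35 |

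So about 1 to 4 of 36 active subjects move to a worst-case high per analyte with no drug effect. One or two subjects with a real, large rise would sit in the same cell.

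**4. How many subjects are high at baseline.** The exclusion limits apply at screening and admit AST or ALT up to 3 x ULN and creatinine up to 2 x ULN. Protocol 6.5.3.4 asks for negative or normal safety tests before aspiration and does not say whether chemistry is included. If it is, few or no transplanted subjects would start high, and the two sections conflict. If it covers infection serology only, they do not. The number cannot be derived from the documents.

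**The case against.** The strongest reply is that the plan contains much more than shift tables. A reader might infer that laboratory change is shown only as shifts and that a rise from 1.2 to 12 x ULN would go unseen. The documents do not support that. The sentence that introduces the shift tables also promises continuous statistics of change, which include the maximum (SAP 8). A change of 10.8 x ULN would probably be the maximum in its arm, a boxplot outlier and a line in a listing. With 48 subjects these outputs can be read by eye.

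An incidence route also exists already. Protocol 6.8.1.7 sends confirmed abnormalities that have changed enough from screening to warrant a change in management to the adverse event form. A further rise in an already high subject qualifies. After dosing, these events are counted by subject and arm under SAP 10.1.1, and Protocol 6.9.1.1 places laboratory changes within treatment-emergent events. This reply largely stands. What remains is that the route depends on investigator judgement and has no numeric threshold.

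Two further replies hold in part. The chance shifts occur at the same rate in the placebo arm, and zero correlation is implausible for repeat values in one person, so the upper end of the range is a bound. And a count by size does not overcome the small control arm. With 3 of 36 against 0 of 12, the two-sided Fisher p-value is (7,140 + 2,376 + 220)/17,296 = 0.56. The added table would describe, not test.

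**Conclusion.** The point holds in a limited form. The plan gives no objective by-arm count of subjects whose laboratory rise exceeds a size set in advance, although the primary objective refers to clinically relevant laboratory changes and the ECG section has such counts. The structural part needs no assumption: reference-range categories cannot show size, in subjects normal or high at baseline.

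The chance figure of about 3% to 12% per analyte rests on the assumed 95% range, five draws, normality and a correlation from 0.9 down to 0. A reader might infer that chance excursions swamp the tables. At about 1 to 4 of 36 per analyte, with a concurrent control, that is too strong for any single test.

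A reader might also infer from the entry limits that many subjects start with raised values. The documents do not show this, and Protocol 6.4.2 and 6.5.3.4 must be reconciled before anyone can say. The trial stays interpretable without the change, which is worth making because it is cheap.

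**What to change.** In SAP 10.1.4, before unblinding, add one table by arm with the number and percentage of safety-population subjects whose worst post-dose value is worse than their own baseline and meets any of these:

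- AST or ALT above 3 x ULN;
- creatinine above 2 x ULN;
- AST, ALT or creatinine at least 2 x the subject's baseline.

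Show each criterion on its own row, so that a doubling within the normal range can be told apart from a value above a ULN multiple. The ULN multiples are the protocol's own entry limits, used here only to tabulate. Keep the shift tables, descriptive statistics, boxplots and listings as planned.

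Separately, state whether the pre-aspiration requirement in Protocol 6.5.3.4 covers chemistry, and reconcile it with exclusions 6 and 7.

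The cost is a few lines of SAP text and one extra table from data already collected. The twofold-baseline cut is a convention with no source in the documents and must be fixed in advance. Thresholds for other analytes are optional.

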10.1.5 Electrocardiograms (ECG)

Heart rate (HR) in beats per minute, QT interval in milliseconds, and QTcF (Fridericia's) interval in milliseconds will be summarized using continuous descriptive statistics by treatment group at each visit. QTcF (Fridericia) will be estimated by the following :

$$\text{QTcF} = \frac{\text{QT}}{(\text{RR})^{1/3}} \quad \text{where RR=60/HR}$$

Change from Baseline to each post-Baseline visit will be also summarized by treatment group. The number and percentage of subjects with changes in QTcF from Baseline of >30 msec and >60 msec as well as the number and percentage of subjects with QTcF values >450 msec will be tabulated at each post-treatment visit.

Note that subjects treated under the original Protocol at the Transplantation Visit will have ECG assessments at 48 hours post-transplantation; subjects treated under Amendment 1 of the Protocol at the Transplantation Visit will have ECG assessments at 22 hours post-transplantation. These time points will be summarized separately.

10.2 Efficacy Analyses

The efficacy endpoints for this study are the ALSFRS-R score, SVC (percent of normal for gender, height, and age) [REDACTED].

The ALSFRS-R is an ordinal, validated rating scale used to evaluate level of impairment of patient with ALS in 12 functional activities. The 12 functional areas further group into four domains that encompass gross motor tasks, fine motor tasks, bulbar functions and respiratory function (Table 3). The ALSFRS-R motor score (gross and fine motor scores combined) will also be assessed.

Each question is graded on a 5-point scale from 0 = unable to do to 4 = normal ability. Summation of all individual answers will be a reported score of 0 = worst to 48 = best. Summation of all answers within a domain will give the domain score. Missing values within a subject and visit will be imputed using the average score for the remainder of the questions within the domain, assuming that at least 50% of the domain questions were answered. If less than 50% of the domain questions were answered, then both the domain score and the total score will be considered missing.

Table 3: ALSFRS-R and Domains

The ALSFRS-R		
Question No	Domain	Functional activity
1	Bulbar	Speech
2		Salivation
3		Swallowing

[figure not shown]
4	Fine Motor	Handwriting
5a		Cutting food and handling utensils without gastrostomy
5b		Cutting food and handling utensils with gastrostomy
6		Dressing and hygiene
7	Gross Motor	Turning in bed and adjusting bed clothes
8		Walking
9		Climbing stairs
10	Breathing	Dyspnea
11		Orthopnea
12		Respiratory Insufficiency

SVC measures the maximum amount of air a patient can exhale in a single breath. SVC is reported as a percent of normal for gender, height, and age. Three measures of SVC are captured at each visit and the percent of normal for gender, height, and age are captured for the maximum of the three SVC measures. The percent of normal for gender, height, and age using the maximum measure at a given visit will be used for summaries.

Descriptive statistics on the observed and change from baseline in the ALSFRS-R total score, ALSFRS-R motor score, and SVC will be summarized at each visit, by treatment group. The analyses will be evaluated for the FAS primarily based on available data (no imputation). Figures presenting the mean ALSFRS-R total and motor scores and SVC score over time by treatment group will be presented. Additionally, figures presenting the ALSFRS-R total and motor scores over time, as separate line plots for each subject will be generated. The change from the Screening Visit measure will be summarized for measures during pre-transplantation. The change from Baseline measure will be summarized for measures post-transplantation. The pre-transplantation slope (change in score per month calculated as the difference between the visit date minus the screening date divided by 30.4375) will be estimated from visits prior to transplantation (including the measure pre-transplantation at the transplantation visit). The post-transplantation slope (change in score per month calculated as the difference between the visit date minus the transplantation date divided by 30.4375) will be estimated from visits post transplantation (including the measure pre-transplantation at the transplantation visit). The analysis of change in slope from pre-transplantation to post-transplantation in ALSFRS-R total and motor and in SVC will be estimated using a two-step model. In the first step, linear regressions will be fitted to each subject's pre-transplantation and post-transplantation data separately; and in the 2nd step, the slopes (pre- and post-transplantation slopes) from the first step will be used as a response variable and treatment, period (0 for pre-transplantation slope and 1 for post-transplantation slope), and treatment by period interaction as explanatory variables in a fixed-effects linear model. The two-way interaction between treatment and period will be used to compare the change in slope

in the active treatment group to the change in slope in the placebo group. The post - pre slope estimate within each treatment group will be used to test the change from pre-transplantation to post-transplantation.

The slopes, pre- and post- transplantation and the difference in slopes pre- and post-transplantation will be tested for normality using the Kolmogorov-Smirnov statistic. If the slopes deviate from normality additional summaries will be presented using a Wilcoxon Rank-Sum test on the slope estimates obtained from the mixed-effects linear model. The above analysis is based upon all data from screening through Week 24 and similar analysis will be repeated through 8-week, 12-week, 16-week follow-up periods for ALSFRS and through 8-week and 16-week follow-up periods for SVC.

To assess the robustness of the analysis results when warranted, the two-step model will be repeated with missing values imputed using multiple imputation methods. The monotone regression method will be performed using the SAS procedure PROC MI.

Note, that repeating the imputation 30 times allows for a better understanding of the additional variability inherent in imputing missing values. ALSFRS-R motor scores will be calculated similarly. The 30 sets each of total and motor ALSFRS-R scores will then be analyzed by standard SAS mixed modeling method as specified earlier. [REDACTED]

The procedure for imputing for SVC is analogous to ALSFRS-R. Again, 30 complete datasets will be generated and the Linear Mixed Model to analyze SVC will be fitted on each of the 30 datasets and the results combined to give yield overall inference.

Each subject's pre and post-treatment slope, standard error, and p-value testing the slope versus 0 will be presented in a listing. Additionally, the percent change in slope (post – pre)/absolute(pre) will be calculated and listed. The frequency and percentage of subjects with at least a 10%, 15%, 20%, 25%, and 30% change (improvement) in slope will be summarized and tested between the treatment groups using Fisher's Exact test. These analyses will be performed for subjects showing improvements in ALSFRS-R, SVC, ALSFRS-R and SVC, ALSFRS-R or SVC over the 8-week, 16-week and 24-week post-transplantation follow-up periods.

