6.2 Full Analysis Set (FAS)

The FAS includes all randomized participants who were randomized.. The FAS will be analyzed based upon treatment group subjects were randomized to. Analysis on the FAS will be considered primary.

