6.3 Modified Full Analysis Set (mFAS)

The original protocol and SAP had planned analysis on the mFAS, which was to include all FAS participants who received any study treatment and had at least 12 Weeks of follow-up. During the blinded data review it was determined that the difference between the FAS and mFAS was only one subject and hence no analyses would be performed on the mFAS.

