showing changes in suicide ideation scores from screening (lifetime measure) to worst on Baseline (pre-transplantation period) and from Baseline to worst post-treatment will also be provided. Data will be reported as available without data imputation.

12. Interim Analyses

There are no interim analyses planned for this study.

13. Deviations from Protocol-Stated Analyses

- [REDACTED]
- [REDACTED]
- [REDACTED]
- Updated mixed linear repeated measures statistical model to be a simple linear regression along with general linear model to compare changes in slopes between treatment groups as described above.
- Added slope analysis for 8-week and 16-week follow-up periods was added for the efficacy endpoints.
- Changed population definitions from the protocol stated definitions by removing analyses on mFAS and PP populations.
- Protocol referred to day of transplantation as Day 0, however in the SAP it is treated as Day 1.
- Changes between the original protocol and Amendment 1 are assumed to not impact any statistical analyses

14. Reporting Conventions

Reporting conventions will adhere when possible to the International Conference on Harmonization (ICH) Guidance E3, "Structure and Content of Clinical Study Reports". All tables and listings will be presented in landscape format. All SAS output for tables and listings will be distributed in PDF files.

15. References

16. SAP Revision History

Section #	Description of Change	Rationale
6	Updated FAS definition and removed mFAS	During the blinded data review it was determined that the difference between the FAS and mFAS was only one subject and hence no analyses would be performed on the mFAS

Section #	Description of Change	Rationale
6	Analysis on PP population is deleted	Due to the small sample size in the study, the 3:1 ratio of randomization between active and placebo and the possibility that a disproportionate number of the subjects may be in the Placebo group, analysis on the PP population will not be performed.
10.2 and 10.3.1	Updated the primary model from mixed-effects linear model to two-step model.	The mixed-effects linear model has restriction on the random effects estimates (slope) which causes the estimated slopes to be either lower or higher than the actual slopes from simple linear regression which was deemed to be more appropriate.

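### The two-step slope model treats each patient's pre- and post-transplantation slopes as independent, so its standard errors and p-values for the change in slope are generally miscalibrated, and the imputation text names a different model

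*SAP*

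**What the plan says.** The protocol (Section 6.9.4.3) planned a mixed linear model with within-subject covariance, the structure chosen by BIC and Kenward-Roger degrees of freedom. SAP Section 13 records the change: "Updated mixed linear repeated measures statistical model to be a simple linear regression along with general linear model".

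SAP Section 10.2 describes the replacement. Step 1 fits separate pre- and post-transplantation regressions for each patient. Step 2 takes both slopes as responses, with treatment, period "and treatment by period interaction as explanatory variables in a fixed-effects linear model". The interaction gives the between-arm test, and the post-minus-pre estimate within each arm gives the within-arm test.

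The pre-dose reading at the transplantation visit belongs to the pre-transplantation slope. It also enters the other regression: the post-transplantation slope "will be estimated from visits post transplantation (including the measure pre-transplantation at the transplantation visit").

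The same section says that the two-step model is repeated after imputation. It then says that the imputed ALSFRS-R scores "will then be analyzed by standard SAS mixed modeling method as specified earlier" and that "the Linear Mixed Model to analyze SVC will be fitted on each of the 30 datasets". If normality fails, it calls for a "Wilcoxon Rank-Sum test on the slope estimates obtained from the mixed-effects linear model".

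SAP Section 8 sets one-sided alpha at 0.10 for all efficacy tests.

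**The concern.** Two slopes from one patient are not independent observations. The variance of their difference is Vpre + Vpost - 2Cov, and a fixed-effects model with only treatment and period terms estimates it as Vpre + Vpost. Two sources of covariance are present and they pull in opposite directions:

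- **Stable progression.** A fast decliner before transplantation tends to remain one, so Cov is positive. Standard errors are then too large, the test is conservative and power is lost.
- **The shared visit.** A chance high reading on the transplantation day flattens the pre slope and steepens the post slope, so Cov is negative. Standard errors are then too small and alpha exceeds 0.10.

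Inference is about right only if the two nearly cancel. The reason in the SAP revision history for dropping the mixed model concerns shrinkage of estimated slopes. It does not justify ignoring the pairing in step 2.

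This model supplies every between-arm and within-arm test and interval for change in slope, and it is reused for the shorter windows, the subgroups and the covariate models. Efficacy is secondary, but protocol Section 6.3.7 treats a slope reduction against placebo as the response to take into Phase III, and the SAP revision history says the 8-week analysis will help design a multi-dose study.

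**Working it through.** **Stated figure.** One-sided 0.10 equals two-sided 0.20: both have critical value z = 1.2816. The SAP's correspondence is correct. The question is whether the model delivers that level.

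**Inputs from the documents.** 36 active and 12 placebo patients; ALSFRS-R at V1, V2, V3 and V5, then weeks 2, 4, 8, 12, 16, 20 and 24; months of 30.4375 days.

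**Assumed inputs.** Visits at weeks -14, -9, -5 and 0 before transplantation; linear decline within each period; independent residuals; complete pairs; slope SD 0.5-1.0 points/month; true pre/post slope correlation 0.5-0.8; residual SD 1-2 points.

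**Formulas.**

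- Model variance of the interaction: (Vpre + Vpost)(1/36 + 1/12) = (Vpre + Vpost)/9.
- True variance: (Vpre + Vpost - 2Cov)/9.
- Model SE / true SE = sqrt[(Vpre + Vpost)/(Vpre + Vpost - 2Cov)].
- Actual alpha ≈ P(Z > 1.291 × ratio), where 1.291 is the 90th percentile of t on 96 - 4 = 92 df. The paired comparison has 48 - 2 = 46 df.

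**Effect of the shared visit.** Sxx is the sum of squared deviations of visit times in months², and a reading's weight in the slope is its deviation divided by Sxx. Before transplantation Sxx is 5.61 and the transplantation-visit weight is +0.287. The error covariance is the product of the pre and post weights, times the residual variance.

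| Window | Sxx post | Weight in post slope | Error covariance / residual variance |
|---|---|---|---|
| 24 wk | 28.3 | -0.087 | -0.025 |
| 16 wk | 10.0 | -0.160 | -0.046 |
| 12 wk | 4.91 | -0.244 | -0.070 |
| 8 wk | 1.85 | -0.435 | -0.125 |

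**Worked case: 24 weeks, slope SD 0.8, correlation 0.8, residual SD 1.5.**

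- Vpre = 0.64 + 2.25/5.61 = 1.041
- Vpost = 0.64 + 2.25/28.3 = 0.719
- Cov = 0.8 × 0.64 - 2.25 × 0.025 = 0.456
- Model SE = sqrt(1.761/9) = 0.442; true SE = sqrt(0.850/9) = 0.307; ratio 1.44
- Actual alpha = P(Z > 1.86) ≈ 0.03

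**Range over the assumed inputs (nominal 0.10).**

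| Window | Model SE / true SE | Actual one-sided alpha |
|---|---|---|
| 24 wk | 1.02-1.83 | 0.009-0.094 |
| 16 wk | 0.97-1.72 | 0.013-0.106 |
| 12 wk | 0.93-1.61 | 0.019-0.115 |
| 8 wk | 0.90-1.41 | 0.034-0.121 |

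With slope SD 0.3, alpha is 0.070-0.110 at 24 weeks and 0.111-0.129 at 8 weeks.

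**Simulation, 20,000 trials per setting.** Settings are (slope SD, correlation, residual SD). Power is for an assumed benefit of 0.5 points/month at 24 weeks.

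| Setting | Alpha 24 wk | Alpha 8 wk | 80% CI coverage 24 wk | 80% CI coverage 8 wk | Power as written vs paired |
|---|---|---|---|---|---|
| 0.5, 0.5, 2 | 0.094 | 0.122 | 81% | 75% | 50% vs 51% |
| 0.8, 0.5, 1.5 | 0.063 | 0.095 | 87% | 81% | 42% vs 52% |
| 0.8, 0.8, 1.5 | 0.034 | 0.079 | 93% | 84% | 41% vs 63% |
| 1.0, 0.8, 1 | 0.011 | 0.034 | 98% | 93% | 31% vs 71% |

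Analysing each patient's post-minus-pre slope gave alpha of 0.095-0.103 throughout. Within-arm tests in the active group were off by the same amount at 24 weeks: 0.094, 0.064, 0.033 and 0.011.

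**Model names.** This part needs no arithmetic. One sentence repeats the two-step model on imputed data. Later sentences give those data to a mixed model described as already specified, and the rank-sum test takes its slopes from a mixed model. The readable SAP specifies no current mixed model, and Section 13 says it was replaced.

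**The case against.** The strongest reply concerns weight. Safety is the primary objective, no sample size was calculated, and efficacy is meant to show trends. In the main range alpha never exceeds 0.121, and at 24 weeks the cost is mainly power in a trial that claims none. Complete-pair point estimates, the Fisher responder tests and the rank-sum test do not use this variance. All of that is true. It limits the consequence but does not defend the intervals and p-values the SAP will report.

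Several qualifications stand:

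- The 24-week test is conservative only given the assumed floor of 0.5 for slope SD and independent residuals. With slope SD 0.3, alpha reaches 0.110. With residual correlation decaying at 0.3-0.5 per month, the upper end of the main range rises from 0.094 to about 0.106.
- The 0.5 points/month benefit is not in the documents. At 8 weeks in the first simulated setting, power is about 33% as written against 29% paired; the written test looks stronger there only because its alpha is inflated.
- The tabulated figures are in ALSFRS-R points. SVC has no readings at weeks 12 and 20, and its slope and residual SDs are unknown, so the point carries over in kind and not in size.
- Redacted text follows the imputation wording, and Section 10.3.1 is not readable. The mixed-model phrases are probably left over from the replaced model, but the readable text does not settle it.

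**Conclusion.** The concern holds. As written, step 2 leaves out a covariance that the SAP's own slope definitions create, and the stated one-sided 0.10 level is not delivered in general. Neither the size nor the direction of the error is fixed by the documents. Under the main assumed range for ALSFRS-R, the 24-week test is between close to nominal and strongly conservative, and the 8-, 12- and 16-week tests run from conservative to mildly anti-conservative. The two sources can also nearly cancel: slope SD 0.5, correlation 0.5 and residual SD 2 leave a net correlation of 0.04 at 24 weeks and almost no error.

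That the model omits the covariance, and that the readable text does not settle the model for the imputed data, follow from the wording alone and rest on no assumption.

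**What to change.** In step 2, analyse one value per patient, the post-transplantation slope minus the pre-transplantation slope, regressed on treatment. Keeping two records with an unstructured 2×2 within-subject covariance and Kenward-Roger degrees of freedom, or a fixed subject effect, would also do. Avoid a random intercept with its variance bounded at zero, because it cannot represent negative correlation. At 8 weeks with slope SD 0.5, correlation 0.5 and residual SD 2, that variance was estimated at zero in 95% of simulated trials and alpha was 0.123, against 0.098 paired.

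State how patients with only one slope are handled: the paired difference drops them and the unstructured model keeps them. This needs saying because "The FAS includes all randomized participants who were randomized", treated or not. Few should be affected, since the blinded review found that "the difference between the FAS and mFAS was only one subject".

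Use the same model for the 8-, 12- and 16-week, subgroup, covariate and imputed-data analyses, and name it consistently in Section 10.2, including as the source of slopes for the rank-sum test. Adding site, the stratification factor, is a separate option that may move the point estimate.

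The cost is one or two sentences in Section 10.2, corrected model names and a small code change. No new data are needed, and with complete pairs and no site term the point estimates do not change.
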